	
variables, treatment condition (active or placebo), time of assessment, condition-by-time, recruitment site, and a site-by-treatment interaction term. A test of the treatment condition will directly test the main research question. Covariates identified by preliminary analysis as potentially confounding due to baseline differences will be added to the model.
 
Given the sample size of 60 per treatment condition, in this multisite, randomized trial using oxygenation index as the primary outcome and measures taken at 6 time points, it is estimated the study will have 80% power to detect a difference between conditions for an effect size as low as 0.43. Using the pilot data from Day 4, for example, this would translate to approximately a difference of 1.29 on the oxygenation index.
 
The primary and secondary endpoints (including clinical and biological data) will be adjusted for SARS-CoV-2 infection as a cause of ARDS, which is adjudicated by the study physicians.

2 Glossary of Abbreviations

Abbreviation	Full Term
AE	Adverse Event
AFC	Alveolar Fluid Clearance
ALI	Acute Lung Injury
ARDS	Acute Respiratory Distress Syndrome
mBAL	Mini-Bronchoalveolar Lavage
CFR	Code of Federal Regulations
cIRB	Central Institutional Review Board
CRF	Case Report Form
DoD	United States Department of Defense
DSMB	Data and Safety Monitoring Board
EAP	Expanded Access Program
ECMO	Extracorporeal Membrane Oxygenation
EUA	Emergency Use Authorization
FDA	Food and Drug Administration
GCS	Glasgow Coma Score
HFOV	High-Frequency Oscillatory Ventilation
HIPPA	Health Insurance Portability and Accountability Act of 1996
hMSCs	Human Mesenchymal Stromal Cells
HS	Hemorrhagic Shock
HSC	Hematopoietic Stem Cells
ICH	International Conference on Harmonization
ICU	Intensive Care Unit
IND	Investigational New Drug
IRB	Institutional Review Board
IV	Intravenous(ly)
KGF	Keratinocyte Growth Factor
LIS	Lung Injury Score
mBAL	Mini Bronchoalveolar Lavage
MSCs	Mesenchymal Stromal Cells
NIH	National Institute of Health
NHLBI	National Heart, Lung and Blood Institute

Abbreviation	Full Term
NLR	Neutrophil:Lymphocyte Ratio
OI	Oxygenation Index
OSCI	Ordinal Scale for Clinical Improvement
PACT	Production Assistance for Cellular Therapy
PAOP	Pulmonary Artery Occlusion Pressure
PBW	Predicted Body Weight
PEC	Pulmonary Endothelial Cell
PEEP	Positive End-Expiratory Pressure
PHI	Protected Health Information
SAE	Serious Adverse Event
SOP	Standard Operating Procedure
VR	Ventilatory Ratio

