11.2 Statistical Methods for Primary and Secondary Endpoints

Descriptive summary statistics (e.g. means and standard deviations, or median with inter-quartile, as appropriate) will be used to summarize the primary and secondary endpoints by study treatment. The primary and secondary efficacy endpoints will also be analyzed using appropriate models.

The primary endpoint, change in the oxygenation index over time, will be compared between treatment conditions using a linear mixed-effects regression model. The model will be estimated using likelihood estimation which will allow the inclusion of all collected data, regardless of the number of assessments available for assessment. Terms in the model will include the two stratification variables, treatment condition (active or placebo), time of assessment, condition-by-time, recruitment site and a site-by-treatment interaction term. A test of the treatment condition will directly test the main research question. Covariates identified by preliminary analysis as potentially confounding due to baseline differences will be added to the model.

The data analysis plan for secondary efficacy and safety endpoints has been provided in the Statistical Analysis Plan.

The primary and secondary endpoints (including clinical and biological data) will be adjusted for COVID-19 infection as a cause of ARDS, which is adjudicated by the study physicians.

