12.6 Analysis for Primary Efficacy Endpoint

The primary endpoint is the changes in the oxygenation index from the baseline to the time-points at 6, 12, 18, 24, 30 and 36 hours after infusion of study product. The oxygenation index will only be calculated when the patient is still being ventilated with positive pressure. If patient is on pressure support, oxygenation index will be treated as missing because the mean airway pressure is not reliable.

Descriptive summary statistics (e.g. means and standard deviations, or median with inter-quartile, as appropriate) will be presented for the oxygenation index values, as well as the changes of oxygenation index from the baseline to each following timepoint by allocated group in modified ITT population.

The change of oxygenation index, by allocated treatment groups in modified ITT Population, will be compared using two linear mixed-effects regression models: unadjusted and adjusted model. Both models will be estimated using maximum likelihood estimation, which will allow the inclusion of all collected data, regardless of the number of assessments available for assessment. All models will include the stratification variables: $\text{PaO}_2/\text{FiO}_2$ ($< 150 \text{ mmHg}$ or $\geq 150 \text{ mmHg}$) and trauma status (trauma vs. non-trauma). Terms in the unadjusted linear mixed-effects regression model will include the two stratification variables, treatment condition (active or placebo), time of assessment (by hour), condition-by-time, recruitment site and a site-by-treatment interaction term. A test of the treatment condition will directly test the main research question. The adjusted linear mixed-effects regression model will include all the variables from the unadjusted model described above plus covariates identified by preliminary analysis as potentially confounding due to baseline differences ($p\text{-value} < 0.20$). The treatment effects may vary with ARDS severity ($\text{PaO}_2/\text{FiO}_2$) or by trauma status, thus the interaction terms will be also included. Both unadjusted and adjusted models will be presented with coefficient with 95% confidence intervals.

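### The primary test is the treatment term of a model with treatment-by-time and site-by-treatment interactions, but no contrast, time coding or site averaging is named, so what it tests depends on coding

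*SAP*

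**What the plan says.** SAP 7.1 sets the endpoint as the decrease in oxygenation index (OI) from baseline across 36 hours, counted from the start of infusion, with readings at 6, 12, 18, 24, 30 and 36 hours. SAP 10 claims 80% power for a standardised effect of 0.43 with 60 patients per arm and six measures.

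SAP 12.6 says the change in OI "will be compared using two linear mixed-effects regression models: unadjusted and adjusted model". Besides the two stratification variables and treatment, the unadjusted model contains "time of assessment (by hour), condition-by-time, recruitment site and a site-by-treatment interaction term". The next sentence is the test rule: "A test of the treatment condition will directly test the main research question". The adjusted model comes after it and adds baseline covariates with p < 0.20. Treatment effects may differ by PaO2/FiO2 "or by trauma status, thus the interaction terms will be also included". On reporting: "Both unadjusted and adjusted models will be presented with coefficient with 95% confidence intervals".

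Protocol 11.2 ends its term list with "recruitment site and a site-by-treatment interaction term. A test of the treatment condition will directly test the main research question", and the synopsis does the same. Both list time of assessment without the words in brackets that the SAP adds. Protocol 11.2 describes a single model: "Covariates identified by preliminary analysis as potentially confounding due to baseline differences will be added to the model". SAP 12.8 describes adjustment for the stratification variables, APACHE III and baseline measures that differ at p < 0.20.

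Neither document says whether hours are numeric or categorical, where time is centred, whether site is fixed or random, how site and strata are coded, or whether the test is a coefficient or a marginal (Type III) test. SAP 12.5 names SAS and Stata only.

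**The concern.** When treatment interacts with other terms, its main-effect coefficient is the treatment difference at the point where those other terms are zero. That point is set by coding. The plan makes this term the primary test without fixing the coding, so two analysts who both follow the SAP can test different hypotheses on the same data, and only some of those hypotheses are the 36-hour endpoint.

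This goes beyond missing detail. Default choices in standard software (numeric hours entered as they stand, or reference-coded factors) lead away from the stated endpoint. SAP 12.7.1 and 12.7.3 model several secondary endpoints in the same way, so the gap passes to them.

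**Working it through.** **Inputs from the documents.** 60 per arm, effect 0.43, 80% power, six measures (SAP 10); two-sided 5% (SAP 12.5); visits at 6 to 36 hours (SAP 7.1); seven sites and an infusion of about 60 to 80 minutes (SAP 5).

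**Assumptions not in the documents.** Unit variance, equal correlation ρ between visits, complete data, equal sites (120/7 = 17.1 patients, 8.57 per arm), normal approximation, and the effect shapes below.

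**Step 1: the plan's own 80%.** For one visit, SE = √(2/60) = 0.183, 0.43/0.183 = 2.355, and power = Φ(2.355 − 1.96) = 65%. For the mean of six visits, SE² = [(1 + 5ρ)/6]/30. Power of 80% needs SE = 0.43/2.802 = 0.1535, so (1 + 5ρ)/6 = 30 × 0.1535² = 0.707 and ρ = 0.65. The documents give no ρ, so the 80% can be matched but not derived. It fits a six-visit average and not a single visit. Because ρ is solved from the 80%, the 80% in step 3 is not independent evidence.

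**Step 2: what the coefficient means.** Write the arm difference at hour t in site s as β + γt + δₛ. The treatment coefficient is β.
- Numeric uncentred hours: β is the difference at t = 0. The infusion is only starting then, and the earliest measured visit is 6 hours later, so this is an extrapolation.
- Categorical hours with a reference visit: β is the difference at that visit. Making site random does not change this.
- Fixed sites with a reference level: β holds for that site only.
- Sum-coded or marginal tests, or hours centred at 21 and averaged over sites: the 6 to 36 hour average.

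**Step 3: size.** The visits have mean 21 and sum of squared deviations 2(15² + 9² + 3²) = 630. At ρ = 0.65:
- Average: SE² = 0.7083/30, so SE = 0.154.
- Hour 0, averaged over sites: SE² = [0.7083 + 21² × 0.35/630]/30 = 0.9533/30, so SE = 0.178.
- Visit 6 h, averaged over sites: SE = 0.183.
- Hour 0, one site (common slope): SE² = 0.7083 × 2/8.57 + 0.245/30 = 0.1734, so SE = 0.416.

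Two effect shapes, each with mean 0.43: constant, and a linear rise from zero (0.43t/21, which is 0.123 at 6 h and 0 at hour 0).

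| Treatment term read as | Power, constant | Power, linear rise |
|---|---|---|
| 6–36 h average, over sites | 80% | 80% |
| Hour 0, over sites | 67% | 5% |
| 6 h visit, over sites | 65% | 10% |
| Hour 0, one site | 18% | 5% |

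For ρ = 0.5 and 0.8, the average has 87% and 73%, and hour 0 over sites with a constant effect has 68% and 67%. The 5% does not depend on ρ, because the quantity tested is zero. With first-order autoregressive correlation of 0.8 or 0.9 and a constant effect, the average has 82% or 74%, and hour 0 over sites has 54% or 58%.

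Simulation (2,000 trials per setting, seven sites of nine per arm, 126 patients) agrees. In table order, it gives 82%, 70%, 66% and 19% for the constant effect, and 81%, 5%, 10% and 5% for the linear rise.

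The shift can also go the other way. For an effect falling from 0.573 at 6 h to 0.287 at 36 h (mean 0.43), the fitted line at hour 0 is 0.43 + 21 × 0.286/30 = 0.63, and the hour-0 test has about 94% power.

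**The case against.** The best reply is that the intent is clear. SAP 7.1 and SAP 12.6 list six discrete visits, SAP 10 counts six measures, and step 1 shows that the power figure fits an average and not a single visit. The bracketed words in the SAP could mean categorical hours, and they are absent from the protocol. The sentence about coefficients governs presentation, not necessarily the test. An experienced analyst might well use a marginal test.

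Most of this stands. A reader might infer that the plan tests the arm difference at hour 0; the documents do not say so, and hour 0 is one plausible reading among several. A reader might also infer that the primary test applies to one PaO2/FiO2-by-trauma stratum. SAP 12.6 attaches the test to the unadjusted model and mentions those interactions only after the adjusted one, so that limitation reaches the adjusted model at most. Nor do the figures show that the trial is underpowered: correlation, site sizes and effect shapes are assumed. Complete data are assumed too, whereas SAP 13.1 expects OI to go missing through death, pressure support or extubation, and nothing here measures that.

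Evidence of intent does not fix the analysis, however. The operative sentence still names a term whose meaning depends on coding. Blinded A/B coding (SAP 12.3) guards against choosing an analysis by direction, but it does not settle which contrast is tested.

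**Conclusion.** The concern holds as one of specification: the primary contrast, the time coding and the averaging over sites are not stated, and admissible readings differ in what they test. Under the stated assumptions, power for the same mean effect of 0.43 SD runs from about 80% for the 6 to 36 hour average down to 67% or 5% at hour 0, depending on effect shape, and to about 18% at one reference site with a constant effect. These figures show scale and do not predict this trial. The defect itself follows from the model terms and does not rest on them. A smaller ambiguity goes with it: SAP 12.6 attaches the test to its unadjusted model without calling that model primary, while Protocol 11.2 describes one model with covariates added.

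**What to change.** In the synopsis, Protocol 11.2 and SAP 12.6, replace the test sentence with: *The primary test is the treatment difference in change in OI averaged with equal weight over 6, 12, 18, 24, 30 and 36 h, with time as a categorical factor, averaged over sites.*

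Then:
- State the site weights (for example, by number of patients) and whether site is fixed or random. Other weights are defensible; what matters is that they are named.
- State that the unadjusted model is primary, or name another, and make Protocol 11.2, the synopsis and SAP 12.8 agree.
- In any model with PaO2/FiO2 or trauma interactions, take the same contrast averaged over strata and report the interactions as heterogeneity analyses.
- Use the matching averaged contrast for the secondary endpoints modelled in parallel (SAP 12.7.1 and 12.7.3).

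The cost is protocol and SAP wording, settled before unblinding. It needs no new data and no extra patients.

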7.6 Randomization and stratification

For this Phase 2b trial, after informed consent is given, an assignment will be made by computer-generated randomization to administer either hMSCs therapy or placebo with a 1:1 allocation to the hMSCs:placebo arms. Randomization will occur during the 2 hour planned baseline stability period and must occur in time to allow the study team to initiate the study product infusion within 14 days of initial ICU admission. The study participant must have an arterial blood gas with a $\text{PaO}_2/\text{FiO}_2$ ratio < 250 with $\text{PEEP} \geq 5 \text{ cm H}_2\text{O}$ within 6 hours of randomization.

Since oxygenation index is the primary endpoint, we would like to minimize imbalances in the hMSC and placebo groups in their initial levels of arterial hypoxemia. Therefore, the randomization plan at each site will be designed to randomize patients by those with a $\text{PaO}_2/\text{FiO}_2 < 150 \text{ mmHg}$ into equal numbers into the hMSC versus placebo arms. The randomization will also be stratified by the presence or absence of trauma.

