10.4.2 Specimen Collection

1. Date and time of specimen collection
2. Time of specimen processing and storage

10.5 *Endpoint Determinations*

1. Vital status at 60 days
2. Brussels Organ dysfunction failures at days 0-14
3. SOFA score at 3 and 7 days
4. Oxygenation index ($\text{PaO}_2/\text{FiO}_2$ and mean airway pressure) at 6, 12, 18, 24, 30 and 36 hours after the initiation of study product infusion as well as on days 2, 3, and 7 if still being ventilated with positive pressure (cannot be calculated if patient is on pressure support, as the mean airway pressure is not reliable)
5. Ventilatory ratio at 6, 12, 18, 24, 30, 36 hours after the initiation of study product infusion, and on days 2, 3, 7
6. Incidence of barotrauma on days 1, 2, 3 and 7
7. Time when patient achieves pressure support ventilation with 5 cmH_2O and 5 cmH_2O positive end-expiratory pressure for 2 hours
8. Time of initiation of unassisted breathing (assuming a patient achieves 48 consecutive hours of unassisted breathing)
9. Need for re-instituting assisted or mechanical ventilation after achieving 48 consecutive hours of unassisted breathing
10. Status 48 hours after initiation of unassisted breathing
11. Need for, timing, and duration of dialysis; change in renal function as measured by creatinine
12. ICU length of stay in calendar days including ICU days after readmission to ICU
13. Hospital length of stay in calendar days
14. Discharge diagnoses and discharge disposition (home, other facility, with or without assisted ventilation)
15. WHO Ordinal Scale of Clinical Assessment at days 7, 14 and 28

10.6 *Assessments After Hospitalization*

A health status questionnaire will be conducted at 28 days, 60 days and 6 months through telephone interviews.

11 Statistical Plan

The Statistical Analysis Plan has been written along with this Protocol and provides the details of the statistical methodologies applied to this Phase 2b trial.

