10 SAMPLE SIZE DETERMINATION

The sample size for this trial will be 60 patients in the hMSCs arm and 60 patients in the placebo arm, for a total of 120 patients with a balanced randomization of patients with $\text{PaO}_2:\text{FiO}_2 < 150$ mmHg. This sample size was determined on the basis of feasibility.

Given the sample size of 60 per treatment condition, in this multisite, randomized trial using oxygenation index as the primary outcome and measures taken at 6 time points, it is estimated the study will have 80% power to detect a difference between conditions for an effect size as low as 0.43. Using the pilot data from Day 4, for example, this would translate to approximately a difference of 1.29 in the oxygenation index.

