12.8 Adjustments for Stratification and SARS-CoV-2 Infection

Analyses of the outcomes will be adjusted for stratification variables (PaO₂/FiO₂ ratio [<150 mmHg or ≥ 150 mmHg] and trauma vs. non-trauma), APACHE III scores at baseline, and baseline measure, where P-value < 0.20 between treatment group.

To better understand the hMSC effects in patient with COVID-19 disease, the primary and secondary endpoints specified in Section 12.6 and 12.7 will also be summarized and conducted in separate linear mixed-effects regression models, in a fashion parallel to the analyses of the above main primary endpoint models, stratified or adjusted by the following binary variables of interest prior to randomization:

- SARS-CoV-2 infection status obtained from medical chart: yes or no
- COVID-19 as a cause of ARDS which is adjudicated by the study physicians: yes or no
- Viral antigen levels measured by NIH lab (PI: [name]): the value will be categorized by greater or less than median value
- Dexamethasone (or equivalent steroid therapy): yes or no
- Other immunomodulatory agents: yes or no
- Anticoagulation and antiplatelet treatments: yes or no
- MSC viability at the time of administration

Furthermore, the primary and secondary endpoints will be analyzed by latent class analysis (LCA) subphenotype using the same procedures described in previous studies (23-26) and adjusted for SARS-CoV-2 infection. In addition, we will test for an interaction between MSC therapy and the subphenotypes for the clinical outcomes.

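### The primary model for change in OI leaves out baseline OI unless the arms happen to differ on it at p<0.20, which costs precision

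*SAP*

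**What the plan says.** SAP 12.6 takes change in OI from baseline at 6, 12, 18, 24, 30 and 36 hours as the response and specifies two linear mixed models. The unadjusted one contains the two stratification variables, treatment, and "time of assessment (by hour), condition-by-time, recruitment site and a site-by-treatment interaction term". Directly after that list the SAP states: "A test of the treatment condition will directly test the main research question". The adjusted model takes the same terms "plus covariates identified by preliminary analysis as potentially confounding due to baseline differences", with p<0.20 as the entry criterion, and treatment interactions with the strata are also mentioned. Baseline OI is named in neither list.

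SAP 12.8 is the only other route. It says outcomes will be adjusted for the stratification variables, "APACHE III scores at baseline, and baseline measure, where P-value < 0.20 between treatment group". It does not define the baseline measure, and it does not say which items the p-value condition covers.

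Protocol 11.2 and the synopsis describe a single model: "Covariates identified by preliminary analysis as potentially confounding due to baseline differences will be added to the model". Protocol 11 defers to the SAP, which "provides the details of the statistical methodologies applied to this Phase 2b trial". Protocol 7.6 explains the PaO2/FiO2 stratification: "we would like to minimize imbalances in the hMSC and placebo groups in their initial levels of arterial hypoxemia". SAP 10 sets 60 patients per arm on grounds of feasibility and states "80% power to detect a difference between conditions for an effect size as low as 0.43", equated to 1.29 OI units.

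**The concern.** The baseline value of the outcome is usually one of the strongest predictors of its later values, and it should be in the model on that ground alone. A p-value for baseline imbalance is a poor way to select it, because that p-value says nothing about how well the covariate predicts outcome. Here the rule also works against itself. Stratifying on PaO2/FiO2 below 150 mmHg makes the arms alike on baseline oxygenation, so the screen will usually leave baseline OI out. The two-level stratum that stays in the model keeps only part of the information and contains no mean airway pressure, which is a component of OI.

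The wording is unsettled as well. If SAP 12.8 ties the baseline measure to p<0.20, baseline OI is normally omitted. If it means always adjusting, it contradicts the term list in SAP 12.6. At stake is the precision of the primary comparison in a trial whose size cannot readily grow.

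**Working it through.** **Inputs from the documents.** 60 per arm, 1:1, six post-baseline times, two-sided 5%, effect size 0.43, 1.29 OI units. The implied SD is 1.29/0.43 = 3.0; the documents do not say whether this is the SD of OI or of change.

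**Assumptions.** Compound symmetry; correlation ρ between any two OI values of 0.5 to 0.8; share R² of baseline OI variance explained by the PaO2/FiO2 stratum of 0.3 to 0.5.

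**The plan's own figure.** A single measure at 0.43 with 60 per arm gives 65.4% power. The mean of six measures has variance factor A = (1+5ρ)/6. This gives 86.9% at ρ = 0.5, 79.9% at 0.65 and 73.2% at 0.8. The stated 80% is attainable, but cannot be confirmed because no correlation is given.

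**How often the screen admits baseline OI.** With arms balanced within strata, the pass probability is P(|Z| > 1.2816/√(1−R²)).
- R² = 0.3: cut-off 1.532, probability 12.6%.
- R² = 0.5: cut-off 1.812, probability 7.0%.

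**Variance with and without baseline OI** (36-hour mean, complete data, stratum in the model, OI SD = 1).
- With baseline OI: V₁ = A − ρ².
- Change score without it: V₀ = A − ρ² + (1−ρ)²(1−R²).

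At ρ = 0.65 and R² = 0.3, A = 0.7083, so V₁ = 0.7083 − 0.4225 = 0.2858 and V₀ = 0.2858 + 0.1225×0.7 = 0.3716. The ratio is 0.769. Standard errors are √(2V/60): 0.1113 without and 0.0976 with. An effect of 0.43 OI SDs gives 97.2% against 99.3% power. In change SDs the effect is 0.43×√(2(1−ρ)) = 0.360, giving 89.8% against 95.8%.

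| ρ | R² | V₁/V₀ | Power at 0.43 OI SD, never → always | Power at 0.43 change SD, never → always |
|---|---|---|---|---|
| 0.5 | 0.3 | 0.656 | 91.0 → 98.3 | 91.0 → 98.3 |
| 0.5 | 0.5 | 0.727 | 93.6 → 98.3 | 93.6 → 98.3 |
| 0.65 | 0.3 | 0.769 | 97.2 → 99.3 | 89.8 → 95.8 |
| 0.65 | 0.5 | 0.824 | 97.9 → 99.3 | 91.7 → 95.8 |
| 0.8 | 0.3 | 0.873 | 99.9 → 100 | 88.6 → 92.3 |
| 0.8 | 0.5 | 0.906 | 99.9 → 100 | 89.7 → 92.3 |

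**Anchored to the plan's 80%.** The columns above start higher than 80%, so near-nil gains at high ρ are partly a ceiling effect. If the change model has exactly 80% power, power after adjustment is Φ(2.8016/√ratio − 1.96). A ratio of 0.656 gives 93%, 0.769 gives 89% and 0.906 gives 84%. At 0.769, the model without baseline OI would need 120/0.769 ≈ 156 patients to match 120 with it.

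**Against the written p<0.20 rule** (simulation, 40,000 trials per cell). Always adjusting gains 0 to 5 power points; for example 91.2 → 95.4 at ρ = 0.65, R² = 0.3 in change SDs. Under the null, rejection is 4.9 to 5.1% never adjusting, 4.9 to 5.0% always adjusting and 3.5 to 4.7% under the screen.

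**With the SAP's other terms.** Adding trauma (10% assumed), seven equal sites, site-by-treatment, treatment-by-time, treatment-by-stratum and treatment-by-trauma terms, and random dropout reaching 0 to 40% by 36 hours:
- the variance ratio for the 36-hour mean is 0.660 to 0.918, a cut of 8 to 34%;
- power gains in OI SDs are 7.1 to 11.7 points (ρ 0.5), 2.4 to 5.3 (0.65) and 0.2 to 0.5 (0.8);
- in change SDs they are 7.1 to 11.7, 5.3 to 8.7 and 2.9 to 4.5.

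If the treatment coefficient is read at hour 0, because treatment-by-time is in the model, the cut is 5 to 21%.

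**The case against.** **The existing model is valid.** A change score adjusted for strata is unbiased on average over randomisations, the PaO2/FiO2 stratum is always in the model, and both models are reported with the analysis done blind. This stands, and it is why the point concerns efficiency. The figures already credit the stratum with 30 to 50% of baseline OI variance.

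**The gain may be small and is uncertain.** ρ, R², compound symmetry and normality are all assumed. At ρ = 0.8 with 0.43 in OI SDs the gain is about nil. The screen pass rate also assumes exact balance; with small blocks within site and some randomised patients never infused it is nearer 10 to 15%. All this stands, and it is why only a range is given. Anchoring to the plan's 80% makes the gain larger, not smaller.

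**Saying there is no bias is too flat.** Conditional on an observed imbalance, the estimate does move. An imbalance at p = 0.20 is 1.2816×√(2/60) = 0.234 SD, or 0.70 OI units at SD 3.0. Multiplied by (1−ρ), and before stratum adjustment, it shifts the estimate by 0.35, 0.25 or 0.14 units at ρ = 0.5, 0.65 or 0.8, which is 27%, 19% or 11% of 1.29. When missing OI was driven by the last OI under one rule in both arms, bias was at most about 0.06 units. In an extreme case, with loss only in the active arm and driven by baseline OI, it was 0.04 to 0.29 units and essentially vanished with baseline OI in the model. These are qualifications, and each favours adjusting.

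**Baseline may already be used as a time-zero response.** SAP 12.6 makes change from baseline the response, so this reading does not fit the text.

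**Conclusion.** The point holds. Baseline OI is not a listed term, and on the natural reading of SAP 12.6 with 12.8 it enters only through an imbalance screen that stratification makes it likely to fail. The expected cost is precision. Under the assumptions above, always adjusting cuts the variance of the 36-hour contrast by 9 to 34% in the simple case. At 0.43 it gains 0 to 7 power points over never adjusting, and 0 to 5 over the written rule. If the change model has the planned 80% power, adjustment brings it to 84 to 93%. The change should be made because it improves the primary analysis at no data cost, not because the current model is invalid. The difference between the protocol's single model and the SAP's two is a lesser matter.

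**What to change.** Before unblinding:

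- In SAP 12.6, with matching text in Protocol 11.2 and the synopsis, include continuous baseline OI in the OI model irrespective of any p-value. Keep the stratification variables and site; this point does not require changing the other listed terms.
- Use the same baseline value that is subtracted to form the change, and define it once: for example, the pre-infusion blood gas (Protocol 9.4) with concurrent FiO2 and mean airway pressure. State a fallback, such as the value nearest randomisation (Protocol 10.2), because Protocol 10.3 does not guarantee mean airway pressure during the stability period.
- Name this model, and one stated treatment contrast from it (for example the average over 36 hours), as the single primary analysis. Treat any p<0.20-screened model as supportive.
- In SAP 12.8, define the baseline measure and say which items the p-value condition covers.

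The cost is SAP wording, a minor protocol amendment to the central IRB, and notice to the DSMB, which asked for an earlier revision of this model (SAP 1). SAP 12.9 plans an interim look at the primary endpoint at 60 patients, so the amendment should record whether that look has happened and that the change was made blind to arm. No new data are needed, since the change score already requires baseline OI.
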